15.12 Urine Protein Creatinine Ratio

Absolute values, CFB and percentage CFB in UPCR at each time point during treatment period will be described.

A shift table will be provided to describe the shift from baseline to highest/lowest post-baseline value during treatment period by the following categories: <0.5 mg/mg, ≥0.5-1 mg/mg, ≥1-2 mg/mg, ≥2-3 mg/mg, ≥3-4mg/mg, ≥4 mg/mg, or missing.

UPCR values containing a modifier will be imputed as described in Appendix 18.13.

A subject data listing, by treatment group and time point (where applicable), will be provided as well. UPCR values containing a modifier such as “<” will be reported as collected in the database and as imputed in the subject data listing.

15.13 HBV DNA

Hepatitis B Virus (HBV) DNA polymerase chain reaction (PCR) testing results will be summarized and listed by treatment group and time point (where applicable). A shift table from baseline to highest post-baseline values including the categories < 20 IU/mL versus ≥ 20 IU/mL will be provided.

15.14 Local Laboratory Results

Local laboratory results that are not described in Section 15.3 will be listed by treatment group and time point (where applicable).

15.15 Drug-induced Liver Injury Kit Results

[figure not shown]
Drug-Induced Liver Injury (DILI) kit results will be listed by treatment group and time point (where applicable).

15.16 COVID-19 Impact

A listing of all subjects affected by the COVID-19 related study disruption (e.g. AEs/SAEs, missed visit/sample not done, treatment/study discontinuation) will be provided by treatment period and treatment group.

16 Analyses of Other Endpoints

CCI

[figure not shown]
CCI

CCI

[figure not shown]
A large black rectangular redaction box covers the majority of the page's content, starting below the header and ending above the footer.

CCI

CCI

CCI

CCI

CCI

17 References

FACIT-Fatigue Scale: http://www.ser.es/wp-content/uploads/2015/03/FACIT-F_INDICE.pdf.

18.1 Definitions of Efficacy Endpoints

18.1.1 BILAG 2004 Disease Activity Index

The BILAG 2004 Disease Activity Index (Yee 2009, Yee 2010) evaluates SLE activity in a number of organ systems, based on the principle of “physician’s intention to treat” (refer to Manual of Procedures). The primary purpose of the BILAG in this study is to assess possible worsening in specific organ systems. Additional analyses of improvements in disease activity as assessed by the BILAG 2004 will also be done.

A separate alphabetic score is assigned to each organ system, corresponding in general to the following definitions:

- BILAG A: Severe disease activity requiring any of the following treatments (e.g., systemic high dose oral CS, intravenous pulse CS, systemic immunosuppressants, or therapeutic high dose anticoagulation in the presence of high dose CS or ≥ 20 mg prednisone). Note that in the context of a CTP with medication restrictions and blinded IMP, the term “requiring” is not taken literally, but indicates that if all else were equal this would be the degree of treatment indicated. It is also understood that some subjects respond to different levels of medication than others, so that in assessing subjects with the BILAG “intent to treat” really means that most subjects with this degree of symptom would require this level of treatment, not necessarily the subject in question.
- BILAG B: Moderate disease activity requiring treatment with systemic low dose oral glucocorticoids, intramuscular or intra-articular or soft tissue CS injection, topical CS or immunosuppressants, or symptomatic therapy such as antimalarials or NSAIDs.
- BILAG C: Mild disease
- BILAG D: System previously affected but now inactive
- BILAG E: System never involved

The BILAG 2004 is evaluated by scoring each of a list of signs and symptom as: improving (1); same (2); worse (3); new (4); not present (0); not done (ND). For some items, appropriate responses may be: Y/N or numerical values where indicated, or Y/N confirm this is due to SLE activity.

All signs and symptoms scored must be due to SLE. Use of a glossary provided with the BILAG 2004 instrument and training of assessors in use of the instrument are essential to obtaining reliable and consistent results.

Use of the BILAG 2004 index for evaluating flares has been identified as a robust way of evaluating the efficacy of drugs; this judgment has been corroborated by external advisors and regulatory authorities.

BILAG assessments should be conducted by a trained evaluator.

18.1.1.1 Constitutional

Grade A:

Pyrexia recorded as 2 (same), 3 (worse) or 4 (new) AND

Any 2 or more of the following recorded as 2 (same), 3 (worse) or 4 (new):

- Weight loss
- Lymphadenopathy/splenomegaly
- Anorexia

Grade B:

Pyrexia recorded as 2 (same), 3 (worse) or 4 (new) OR

Any 2 or more of the following recorded as 2 (same), 3 (worse) or 4 (new):

- Weight loss
- Lymphadenopathy/splenomegaly
- Anorexia

BUT do not fulfil criteria for Grade A

Grade C

Pyrexia recorded as 1 (improving) OR

One or more of the following recorded as > 0:

- Weight loss
- Lymphadenopathy/Splenomegaly
- Anorexia

BUT does not fulfil criteria for Grade A or B

Grade D

If criteria for Grade A or B or C are not fulfilled, then subject is by default in Grade D.

18.1.1.2 Mucocutaneous

Grade A

Any of the following recorded as 2 (same), 3 (worse) or 4 (new):

- Skin eruption - severe
- Angio-oedema - severe
- Mucosal ulceration - severe
- Panniculitis/Bullous lupus - severe
- Major cutaneous vasculitis/thrombosis

Grade B

Any Grade A features recorded as 1 (improving) OR

Any of the following recorded as 2 (same), 3 (worse) or 4 (new):

- Skin eruption - mild
- Panniculitis/Bullous lupus - mild

- Digital infarcts or nodular vasculitis
- Alopecia - severe

Grade C

Any Grade B features recorded as 1 (improving) **OR**

Any of the following recorded as > 0:

- Angio-oedema - mild
- Mucosal ulceration - mild
- Alopecia - mild
- Periungual erythema/chilblains
- Splinter haemorrhages

Grade D

If criteria for Grade A or B or C are not fulfilled, then subject is by default in Grade D.

18.1.1.3 Neuropsychiatric

Grade A

Any of the following recorded as 2 (same), 3 (worse) or 4 (new):

- Aseptic meningitis
- Cerebral vasculitis
- Demyelinating syndrome
- Myelopathy
- Acute confusional state
- Psychosis
- Acute inflammatory demyelinating polyradiculoneuropathy
- Mononeuropathy (single/multiplex)
- Cranial neuropathy
- Plexopathy
- Polyneuropathy
- Status epilepticus
- Cerebellar ataxia

Grade B

Any Grade A features recorded as 1 (improving) **OR**

Any of the following recorded as 2 (same), 3 (worse) or 4 (new):

- Seizure disorder
- Cerebrovascular disease (not due to vasculitis)
- Cognitive dysfunction
- Movement disorder
- Autonomic disorder
- Lupus headache - severe unremitting
- Headache due to raised intracranial hypertension

Grade C

Any Grade B features recorded as 1 (improving)

Grade D

If criteria for Grade A or B or C are not fulfilled, then subject is by default in Grade D.

18.1.1.4 Musculoskeletal

Grade A

Any of the following recorded as 2 (same), 3 (worse) or 4 (new):

- Severe Myositis
- Severe Arthritis

Grade B

Any Grade A features recorded as 1 (improving) **OR**

Any of the following recorded as 2 (same), 3 (worse) or 4 (new):

- Mild Myositis
- Moderate Arthritis/Tendonitis/Tenosynovitis

Grade C

Any Grade B features recorded as 1 (improving) **OR**

Any of the following recorded as > 0:

- Mild Arthritis/Arthralgia/Myalgia

Grade D

If criteria for Grade A or B or C are not fulfilled, then subject is by default in Grade D.

18.1.1.5 Cardiorespiratory

Grade A

Any of the following recorded as 2 (same), 3 (worse) or 4 (new):

- Myocarditis/Endocarditis + Cardiac failure
- Arrhythmia
- New valvular dysfunction
- Cardiac tamponade
- Pleural effusion with dyspnoea
- Pulmonary haemorrhage/vasculitis
- Interstitial alveolitis/pneumonitis
- Shrinking lung syndrome
- Aortitis
- Coronary vasculitis

Grade B

Any Grade A features recorded as 1 (improving) **OR**

Any of the following recorded as 2 (same), 3 (worse) or 4 (new):

- Pleurisy/Pericarditis
- Myocarditis - mild

Grade C

Any Grade B features recorded as 1 (improving)

Grade D

If criteria for Grade A or B or C are not fulfilled, then subject is by default in Grade D.

18.1.1.6 **Gastrointestinal**

Grade A

Any of the following recorded as 2 (same), 3 (worse) or 4 (new):

- Peritonitis
- Lupus enteritis/colitis
- Intestinal pseudo-obstruction
- Acute lupus cholecystitis
- Acute lupus pancreatitis

Grade B

Any Grade A feature recorded as 1 (improving) **OR**

Any of the following recorded as 2 (same), 3 (worse) or 4 (new):

- Abdominal serositis and/or ascites
- Malabsorption
- Protein losing enteropathy
- Lupus hepatitis

Grade C

Any Grade B features recorded as 1 (improving)

Grade D

If criteria for Grade A or B or C are not fulfilled, then subject is by default in Grade D.

18.1.1.7 Ophthalmic

Grade A

Any of the following recorded as 2 (same), 3 (worse) or 4 (new):

- Orbital inflammation/myositis/proptosis
- Keratitis - severe
- Posterior uveitis/retinal vasculitis - severe
- Scleritis - severe
- Retinal/choroidal vaso-occlusive disease
- Optic neuritis
- Anterior ischaemic optic neuropathy

Grade B

Any Grade A features recorded as 1 (improving) **OR**

Any of the following recorded as 2 (same), 3 (worse) or 4 (new):

- Keratitis - mild
- Anterior uveitis
- Posterior uveitis/retinal vasculitis - mild
- Scleritis - mild

Grade C

Any Grade B features recorded as 1 (improving) **OR**

Any of the following recorded as > 0:

- Episcleritis
- Isolated cotton-wool spots (cytoid bodies)

Grade D

If criteria for Grade A or B or C are not fulfilled, then subject is by default in Grade D.

18.1.1.8 Renal

Items recorded as “Not SLE related” won’t be considered for the scoring of the RENAL Grade. When an item is ticked “Not SLE related” this means that the item is considered as Normal, no grading. This item does not have to be considered as missing.

Grade A

Two or more of the following **providing 1, 4 or 5 is included**:

1. Deteriorating proteinuria (severe) defined as

- (a) urine dipstick increased by ≥ 2 levels; **or**
- (b) 24 hour urine protein > 1 g that has not decreased (improved) by $\geq 25\%$; **or**
- (c) urine protein-creatinine ratio > 100 mg/mmol that has not decreased (improved) by $\geq 25\%$ **or**
- (d) urine albumin-creatinine ratio > 100 mg/mmol that has not decreased (improved) by $\geq 25\%$

(b) and (d) are not measured in this study and will be disregarded from grade derivation.

(a) will not be used in grade derivation neither, see the paragraph 'Notes' at the end of the Renal grade section.

2. Accelerated hypertension
3. Deteriorating renal function (severe) defined as
 - (a) plasma creatinine > 130 µmol/l and having risen to > 130% of previous value; **or**
 - (b) GFR < 80 ml/min per 1.73 m² and having fallen to < 67% of previous value; **or**
 - (c) GFR < 50 ml/min per 1.73 m², and last time was > 50 ml/min per 1.73 m² or was not measured.
4. Active urinary sediment
5. Histological evidence of active nephritis within last 3 months
6. Nephrotic syndrome

Grade B

One of the following:

1. One of the Grade A feature
2. Proteinuria (that has not fulfilled Grade A criteria)

- (a) urine dipstick which has risen by 1 level to at least 2+; **or**
- (b) 24 hour urine protein ≥ 0.5 g that has not decreased (improved) by ≥ 25%; **or**
- (c) urine protein-creatinine ratio ≥ 50 mg/mmol that has not decreased (improved) by ≥ 25%; **or**
- (d) urine albumin-creatinine ratio ≥ 50 mg/mmol that has not decreased (improved) by ≥ 25%

(b) and (d) are not measured in this study and will be disregarded from grade derivation.

(a) will not be used in grade derivation neither, see the paragraph 'Notes' at the end of the Renal grade section.

3. Plasma creatinine > 130 µmol/l and having risen to ≥ 115% but ≤ 130% of previous value

Grade C

One of the following:

1. Mild/Stable proteinuria defined as
 - (a) urine dipstick ≥ 1+ but has not fulfilled criteria for Grade A & B (used only if UPCR result is not available); **or**
 - (b) 24 hour urine protein > 0.25 g but has not fulfilled criteria for Grade A & B ; **or**
 - (c) urine protein-creatinine ratio > 25 mg/mmol but has not fulfilled criteria for Grade A & B; **or**
 - (d) urine albumin-creatinine ratio > 25 mg/mmol but has not fulfilled criteria for Grade A & B
2. Rising blood pressure (providing the recorded values are > 140/90 mm Hg) which has not fulfilled criteria for Grade A & B, defined as
 - (a) systolic rise of ≥ 30 mm Hg; **and**
 - (b) diastolic rise of ≥ 15mm Hg

(b) and (d) are not measured in this study and will be disregarded from grade derivation.

(a) will not be used in grade derivation neither, see the paragraph 'Notes' at the end of the Renal grade section.

Grade D

If criteria for Grade A or B or C are not fulfilled, then subject is by default in Grade D.

Notes:

Although albumin-creatinine ratio and protein-creatinine ratio are different, the same cut-off values are used for both in this index. However, albumin-creatinine ratio is not collected and therefore not used. Urine dipstick results will not be used for BILAG scoring due to the unreliable results of urine dipstick for urine protein and lack of correlation with UPCr values (e.g., normal, ++ and +++ for urine protein by urine dipstick were reported in subjects with normal or high UPCr values).

When the criterion is evaluated by comparison with a previous assessment (i.e. deteriorating proteinuria, deteriorating renal function, evolution of plasma), the value at the previous visit will be taken. As a consequence, the RENAL grade cannot be derived at screening visit.

18.1.1.9 Haematological

Items recorded as “Not SLE related” won’t be considered for the scoring of the HAEMATOLOGICAL Grade.

Grade A

TTP recorded as 2 (same), 3 (worse) or 4 (new) **OR**

Any of the following:

- Evidence of haemolysis and Hemoglobin < 8 g/dl
- Platelet count < 25 x 10⁹/l

Grade B

TTP recorded as 1 (improving) **OR**

Any of the following:

- Evidence of haemolysis and Hemoglobin 8 - 9.9 g/dl
- Hemoglobin < 8 g/dl (without haemolysis)
- White cell count < 1.0 x 10⁹/l
- Neutrophil count < 0.5 x 10⁹/l
- Platelet count 25 - 49 x 10⁹/l

Grade C

Any of the following:

- Evidence of haemolysis and Hemoglobin ≥ 10 g/dl
- Hemoglobin 8 – 10.9 g/dl (without haemolysis)
- White cell count 1 - 3.9 x 10⁹/l
- Neutrophil count 0.5 - 1.9 x 10⁹/l
- Lymphocyte count < 1.0 x 10⁹/L
- Platelet count 50 - 149 x 10⁹/l
- Isolated Coombs’ test positive

Isolated Coombs’ test will not be considered missing if not done.

Grade D

If criteria for Grade A or B or C are not fulfilled, then subject is by default in Grade D.

Handling of missing items for organ specific scores:

It is anticipated that there are no missing items for the following clinical organ systems: constitutional, mucocutaneous, neuropsychiatric, musculoskeletal, cardiorespiratory, gastrointestinal and ophthalmic.

For renal and haematological organ systems, “Not SLE related” items will not be considered as missing values and will therefore not be considered for the scoring of the organ domain grade. Missing items (including ‘Not done’) will be imputed using the value carried forward from previous analysis visit (only value assessed post-Day 1 dose [i.e. after baseline] can be used for imputation). For renal grade, UPCR will be the only parameter to consider assessing proteinuria. The following logic will be applied: if UPCR is missing (including ‘Not done’), then missing UPCR (and attribution to SLE) will be imputed using the value carried forward from previous analysis visit.

If there are missing items that lead to a missing grade for one or two of the laboratory organ domains, the missing domain grade will be imputed using the value carried forward from previous analysis visit. In such case, BILAG flare will be assessed based on domain grades that were not carried over from previous visit (i.e. excluding the renal and/or haematological domain grade).

If a subject completely missed a visit, the BILAG grades from previous analysis visit will be used and BILAG flare will be derived as missing.

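### A missing UPCR is filled with the previous visit's value and then compared with that same value, so a falling proteinuria can be graded up (C to B, or B to A with a second Grade A feature) without a new measurement

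*SAP*

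**What the plan says.** UPCR is the only measure of proteinuria used for the renal BILAG grade (SAP 18.1.1.8 and 18.1.1.9). Two of its criteria depend on change:

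- Grade A feature 1: "urine protein-creatinine ratio > 100 mg/mmol that has not decreased (improved) by" 25% or more.
- Grade B: "urine protein-creatinine ratio ≥ 50 mg/mmol that has not decreased (improved) by ≥ 25" per cent.

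For criteria judged against an earlier assessment, 18.1.1.8 says that "the value at the previous visit will be taken". Grade A needs "Two or more of the following" listed features, including feature 1, 4 or 5. Grade B is reached with "One of the Grade A feature". An improving UPCR above 25 mg/mmol with no other feature is Grade C.

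If UPCR is missing or not done, "missing UPCR (and attribution to SLE) will be imputed using the value carried forward from previous analysis visit". There is one limit: "only value assessed post-Day 1 dose [i.e. after baseline] can be used for imputation".

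The SAP has two safeguards against flares that arise from carried data. If missing items leave a laboratory domain without a grade, the grade is carried forward, and "In such case, BILAG flare will be assessed based on domain grades that were not carried over from previous visit". If the whole visit is missed, grades are carried forward and flare is set to missing.

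For the renal and haematological domains, 14.2.1 and 14.3.2.1 count a step from C to B or from B to A towards flare.

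**The concern.** A carried-forward value is normally neutral because it leaves the subject where they were. Here it is not, because the grade depends on change as well as level. At the observed visit the subject gets credit for a fall of 25% or more. At the next visit the same number, measured against itself, loses that credit and the grade rises.

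The affected outcomes are:

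- **Time to first severe (BILAG A) flare**, a key secondary endpoint in the hierarchy of 14.1.2.4, if the step reaches A. The severe flare rate in 14.3.2 is affected in the same way.
- **SRI-4 and SRI-6 at Week 52**, through criterion 3 in 14.1.1, if the resulting A or B was not present on Day 1. A new A makes the subject a non-responder. A new B uses up the single new B allowed.
- **BICLA** (18.1.8): a Day 1 renal B that had improved to C returns to B if the Week 52 UPCR is missing.
- **The numeric BILAG total** (18.1.1.10): C to B adds 8 − 1 = 7 points.

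The subjects exposed are those whose proteinuria was improving.

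**Working it through.** The SAP gives no figure to reproduce on this point. The check applies the grading rules of 18.1.1.8 to short UPCR sequences.

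**Inputs.** The cut-offs are > 100 (feature 1), ≥ 50 (Grade B) and > 25 mg/mmol (Grade C). The improvement threshold is a 25% fall. The comparator is the previous visit. Active urinary sediment serves as the example of a second Grade A feature, present at both visits.

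**Formula.** Fall at visit k = (U at k−1 − U at k) / U at k−1. If UPCR is missing at visit k+1, the imputed value is U at k, and the fall is (U at k − U at k) / U at k = 0%. This is below 25% whatever the data, so the change condition always holds and only the level cut-off is left.

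| UPCR at k−1, k (mg/mmol) | Fall at k | Second Grade A feature | Grade at k | Grade at k+1, UPCR carried |
|---|---|---|---|---|
| 200, 120 | 80/200 = 40% | none | C | B |
| 200, 120 | 40% | sediment | B | A |
| 200, 140 | 60/200 = 30% | none | C | B |
| 200, 140 | 30% | sediment | B | A |
| 100, 60 | 40/100 = 40% | none | C | B |
| 100, 60 | 40% | sediment | B | B |
| 120, 80 | 40/120 = 33% | none | C | B |
| 120, 80 | 33% | sediment | B | B |
| 70, 40 | 30/70 = 43% | none | C | C |

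The C-to-B step therefore needs a carried value of at least 50. The B-to-A step needs a carried value above 100 and a second Grade A feature. With carried values from 50 to 100 and sediment present, the grade stays B.

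**Do the safeguards apply?** The first needs a missing domain grade. Once a UPCR has been carried forward, the domain can be graded, so the condition is not met. The second needs a wholly missed visit, and here the subject attended. A subject who misses the whole visit can have no flare recorded, while one who attends and lacks only the urine result can.

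**What would observed data have given?** Take 200, 140, then a measured value:

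- Fall of 0% or 10% (140 or 126): B, or A with sediment. This equals the carried-forward grade.
- Fall of 25% (105): C, or B with sediment. The carried-forward grade is one step too high.

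Near a cut-off, a smaller further fall is enough. From 60, any fall of more than 10/60 = 16.7% takes UPCR below 50. From 120 with sediment, a fall of 20/120 = 16.7% brings it to 100, which is no longer above 100.

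**The case against.** The strongest defence is that carry-forward assumes no change, and a measured plateau at 120 after 200 to 120 is also graded B. On that view the rule gives what its assumption implies. This stands in part: the upgraded grade cannot be called false in every case. But the plateau is assumed, not observed, and in its other two carry-forward routes the SAP declines to count flares from unobserved data.

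Section 14.2.1 also has the EAC review the dry-run BILAG dataset, which might catch such cases. The SAP states no rule for an imputed UPCR, however, and a program that applied these rules would be correct as coded. The EAC Charter is not shown.

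A reader might infer more than the document supports:

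- *That a missed urine sample alone produces a severe flare.* It does not. Proteinuria alone gives at most B, and a single new B is a mild flare under 14.3.2.1. It becomes moderate only with a second new or worse B.
- *That the flare exclusion can never be reached.* It can: with no post-Day 1 UPCR to carry, the item may stay missing and leave the grade missing.
- *That any upgrade at Week 52 costs an SRI response.* It matters only if the grade is new relative to Day 1, and one new B is allowed.
- *That creatinine has a mirror-image defect.* A carried creatinine shows no rise, but neither would a stable measured one, and no grade is raised.

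**Conclusion.** The rule is wrong as written. At an attended visit with UPCR missing and a post-Day 1 value to carry, the change criterion is met by construction and the renal grade can rise without a measurement. The reach is limited to subjects with a fall of at least 25% at the previous visit and a carried UPCR of at least 50 mg/mmol (C to B), or above 100 mg/mmol with a second Grade A feature (B to A, a severe flare).

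The grade is false only if the unmeasured UPCR would have fallen again by 25% or more, or past the cut-off where the carried value lies close to it. The SAP does not give the rate of missing UPCR or the number of subjects in these ranges, so neither the number affected nor any shift in a treatment comparison can be estimated. The conclusion assumes that the comparator visit is the visit the value was carried from, which is the plain reading of 18.1.1.8 and 18.1.1.9.

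**What to change.** Add to 18.1.1: when UPCR is carried forward, the change-from-previous proteinuria criteria are not re-evaluated. The previous visit's proteinuria criterion result is carried forward, and the renal domain is graded from that result plus the items observed at the visit. A renal step that rests on the carried-forward UPCR is not counted as a flare. Renal grades and flares based on observed items still count.

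With this rule, 200 to 120 to missing stays C, or B with sediment.

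The rule should act on the proteinuria criterion only. Carrying the whole renal grade and dropping the domain from flare assessment would discard real events, for example a Grade A reached from observed active sediment and accelerated hypertension at a visit without UPCR.

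Report how many renal grades, flares, and SRI and BICLA responses change. This SAP version postdates review of the primary analysis, so a re-derivation of those results should be labelled post hoc in the CSR, as section 4 requires. The cost is a short addition to the text, a programming change and one comparison table, with no new data collection.
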